9.7.1.4.3 Vital signs

Vital signs assessments will include: Systolic and diastolic blood pressure, pulse, O_2 saturation, oral temperature and respiratory rate.

Measurements will be recorded in the supine position after 5 minutes (mins) rest. Blood pressure, pulse, O₂ saturation and temperature will be measured using an automated validated device, with an appropriately sized cuff.

9.7.1.4.4 12-lead ECG

12-lead ECG assessments will include: Heart rate, PR interval, QRS width, QT interval, and OTcB interval.

ECGs will be recorded in the supine position after 5 mins rest.

ECG recordings will be made using a MAC 5500 or equivalent. Each ECG trace should be labelled with the study number, subject initials and subject number. An investigator will

Confidential Page 56 of 73

provide an interpretation of each tracing. Clinically significant abnormalities should be recorded on the AE page.

9.7.1.4.5 Concomitant Medication

All concomitant medication taken during the screening period and between first dose and the Post-Study Visit will be recorded in the subject's CRF (see Section 9.6.7).

9.7.1.4.6 Spirometry

All spirometry evaluations should follow the recommendations of the ATS/ERS 2005^[13].

The spirometry equipment used during the trial must meet or exceed the minimal ATS/ERS recommendations for diagnostic spirometry equipment as defined in the guideline. Calibration of the spirometry equipment is mandatory and must be performed before the first study measurement. All calibration reports and subject spirometry reports should be stored as source data. All staff conducting the spirometry tests must have received appropriate training that must be documented.

All spirometry manoeuvres should be performed in sitting position whilst wearing nose-clips. At least three acceptable manoeuvres should be performed for each time point, and the results must meet within-test and between-test criteria for acceptability. A maximum of six manoeuvres should be performed at any time point.

Spirometry assessments will include: Forced Expired Volume in 1 second (FEV1), Forced Vital Capacity (FVC) and FEV1/FVC.

9.7.2 Appropriateness of Measurements

All measurements performed in the study are standard measurements.

The total volume of blood to be collected from each subject during the study (approximately 177 mL in Part 1 and 242 mL in Part 2) is considered acceptable.

9.7.3 Primary Efficacy Variable(s)

Not applicable

9.7.4 Drug Concentration Measurements

Plasma samples for drug concentration measurements will be analysed by the Bioanalytical Unit at Simbec according to applicable local SOPs.

9.7.4.1 Pharmacokinetic Blood Sampling

Blood samples (4 mL) for determination of TD139 plasma levels will be taken into K2 EDTA tubes at the times specified in Table 9.7.1 and Table 9.7.2:

Immediately upon sampling the sample will be identified with a bar coded label bearing details of study number, subject number, sampling time point, sample type and a unique 9 digit identification number. The sample will be separated by centrifugation at 1500xg and 4°C for 10 mins. Two (2) equal aliquots of plasma will be transferred to polypropylene tubes labelled identically to the original blood sample and stored at approximately -20°C pending

Confidential Page 57 of 73

analysis. The time at which samples are taken, received into the separating room and placed in the freezer will be recorded in the study documentation.

9.7.4.2 Drug concentration measurements in BAL

BAL samples will also be collected for determination of TD139 concentrations in alveolar macrophages and BAL fluid (saline).

See Section 9.7.5.3 for full details of the BAL collection and handling.

9.7.5 Pharmacodynamics

9.7.5.1 Exhaled Breath Condensate Sampling

Exhaled breath condensate samples will be collected using a commercially available device. The subject will be required to breathe into the device for approximately 10 minutes whilst in a seated position.

Samples will be analysed by the University of Rochester, New York. Specific instructions on sample collection, handling, and shipment will be provided in a set of sampling instructions to each site.

9.7.5.2 Galectin-3 Blood Sampling

Blood samples (3 mL) for determination of galectin-3 plasma levels will be taken into K2 EDTA tubes at the times specified in Table 9.7.1 and Table 9.7.2:

Immediately upon sampling the sample will be identified with a bar coded label bearing details of study number, subject number, sampling time point, sample type and a unique 9 digit identification number. The sample will be separated by centrifugation at 1500xg and 4°C for 10 mins. Two (2) equal aliquots of plasma will be transferred to polypropylene tubes labelled identically to the original blood sample and stored at approximately -20°C pending analysis. The time at which samples are taken, received into the separating room and placed in the freezer will be recorded in the study documentation.

9.7.5.3 Peripheral Blood Flow Cytometry Blood Sampling

Peripheral blood flow cytometry will be performed by the University of Edinburgh on the same sample that is collected for pharmacogenetic analysis (mRNA). See Section 9.7.6 for details.

9.7.5.4 Bronchoalveolar Lavage (BAL)

In Part 2 only, BAL fluid samples will be collected for analysis of:

- Macrophage morphology,
- Ex-vivo macrophage function,
- Macrophage phenotypic and mRNA expression pattern,
- BAL analysis of soluble markers.

GB-HV-01 Clinical Study Protocol Confidential RD 676/25641 Version: FINAL 6.0 / 05 April 2016 Page 58 of 73

BAL samples will also be collected for determination of TD139 concentrations in alveolar macrophages and BAL fluid (saline) (see Section 9.7.4.2).

BAL will be performed by flexible bronchoscopy at each centre's local facility. Specific instructions for performing the bronchoscopy and collecting the BAL samples will be provided in a standard operating procedure, to ensure that there is consistency in technique between sites. Where possible, the procedure will be performed by the same site Investigator.

Detailed information on sample handling and shipment requirements will also be contained in the standard operating procedure.

9.7.6 Pharmacogenetics

The study includes a pharmacogenetic component. This is mandatory in order for the subject to participate in the study.

A 10 mL whole blood sample will be collected into an EDTA tube at the times specified in Table 9.7.1 and Table 9.7.2. After collection, the sample will be inverted several times to prevent clotting. These samples will be shipped to the University of Edinburgh for mRNA analysis.

In addition a 20ml blood sample will be collected at the times specified in Table 9.7.1 and Table 9.7.2. After collection PBMCs will be extracted by density centrifugation and frozen pending analysis. These samples will be shipped to the University of Edinburgh for analysis of IPF gene signatures.

Full information on sample collection, handling, and shipment will be contained in a set of study Pharmacogenetic sampling instructions. The sample collection date and exact time must be entered on the sample collection CRF page.

Macrophage phenotypic and mRNA expression pattern analysis will also be performed in BAL fluid samples at the University of Edinburgh. See Section 9.7.5.4 for details.

9.8 Data Quality Assurance

At the time the study is initiated, a representative of the Sponsor will thoroughly review the Final Protocol and CRFs with the Investigator and staff. During the course of the study the Monitor will visit each Clinical site regularly to check the completeness of the subjects records (including the Volunteer (Subject) Master Files (**Part 1**), Patient Hospital Notes (**Part 2**), laboratory and ECG print-outs), the accuracy of entries into the CRFs, the adherence to the Final Protocol and to ICH GCP^[3], the progress of enrolment and also to ensure the storage, handling and accountability of the IMP. The Investigator and key study personnel will be available to assist the Monitor during these visits.

The Investigator will give the Monitor, Auditor(s), the REC, and the MHRA direct access to relevant clinical records to confirm their consistency with the CRF entries. No information in these records about the identity of the subjects will leave the Clinical sites. The Sponsor will maintain the confidentiality of all subject records.

Study data will be fully documented in the CRFs, subject diaries (Part 2) and study log-books. Dated signatures will be given to account for all interventions in the study by research staff.

GB-HV-01 Clinical Study Protocol Confidential RD 676/25641 Version: FINAL 6.0 / 05 April 2016 Page 59 of 73

Source data is all information in original records and certified copies of original records of clinical findings, observations, or other activities in a clinical study necessary for the reconstruction and evaluation of the study. Source data are contained in source documents (original records or certified copies).

For the purposes of Part 1 the source data will be recorded as detailed in Table 9.8.1.

 Table 9.8.1
 Summary of Source Documentation Location (Part 1)

D-4-	Source Document						
Data	Volunteer Master File	Case Report Form					
Evidence of healthy subject status for entry into clinical study	X						
Demographic Data		X					
Medical History	X						
Inclusion and Exclusion Criteria		X					
Informed consents ¹	X	X					
Subject participation in the clinical study		X					
Subject number in the clinical study		X					
Adverse Events		X					
Previous and on-going therapy	X						
Concomitant therapy		X					
Results of study examinations (e.g. ECGs, Vital signs and Laboratory Safety Tests) ²		X					
Study Visit dates		X					
Administration of study medication		X					
Plasma PK sample collection times		X					

Copies of the Informed Consent Form should be present in the volunteer master file. The original Informed Consent Forms will be maintained in the study officer file during the clinical phase and will then be transferred to the Trial manager for archiving with the Investigator Site File at the end of the study.

Table 9.8.1 (Part 1) indicates where source data will be recorded but for completeness the following information should also be recorded in the volunteer master file/patient hospital notes:

- Clinical Study code.
- Study visit dates (pre-dose; post-dose).
- IMP administration (date of last dose).
- Results of any key safety and efficacy measures from the clinical study that should be noted in the opinion of the Investigator.
- Any concomitant medications used to treat the subject during the study that should be noted in the opinion of the Investigator.

For **Part 2** a Summary of Source Documentation Location table will be inserted into the study monitoring plan.

The data collected in the CRFs during the study will be subject to quality control checking by clinical staff prior to sign off.

Part 1 of the study will be subject to an independent audit by the Simbec Quality Assurance Unit as outlined in Simbec SOP BD/324/9/01.

The 12-lead ECG trace and Laboratory Safety Test print-out will be stored in the case report form.

GB-HV-01 Clinical Study Protocol Confidential RD 676/25641 Version: FINAL 6.0 / 05 April 2016 Page 60 of 73

Independent clinical quality assurance audits may be performed at any time during or following completion of the Study by the Sponsor, or its authorised agents and Regulatory Authorities and/or the REC.

9.9 Statistical Methods and Determination of Sample Size

9.9.1 Statistical and Analytical Plan

9.9.1.1 Primary and Secondary Variables for Assessment

The primary safety assessment variables will be the vital signs data, ECG data, laboratory data and the adverse events reported.

The secondary pharmacokinetic variables will be the following non-compartmental pharmacokinetic end-points:

	Politica
• C _{max}	Maximum plasma concentration
• t _{max}	The time to maximum observed concentration sampled during
	a dosing interval
 λ_z 	Elimination rate constant
• t _{1/2}	Terminal half-life
• AUC _{0-t}	Area under the plasma concentration-time curve (AUC) from the
	time of dosing to the time of the last observed concentration
• AUC _{0-τ}	Area under the plasma concentration-time curve (AUC) from the
	time of dosing to time t at steady state
• AUC _{0-inf}	The area under the curve (AUC) extrapolated to infinity from dosing
	time, based on the last observed concentration
• CL/F	Plasma clearance, calculated as Dose / $AUC_{0\text{-}inf}$
AUC% extrapolated	Residual area

The secondary pharmacodynamic variables will be the peripheral blood flow cytometry data and galectin-3 plasma concentration data.

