9.6.7 Selection of Doses in the Study

For Part 1, the planned doses of TD139 to be studied are: 0.15mg, 1.5mg, 3mg, 10mg, 20mg and 50mg. The maximum dose of TD139 (50 mg) will not be exceeded.

The planned dose levels have been selected following review of non-clinical pharmacokinetic, safety pharmacology and toxicology data.

Pharmacokinetic, toxicokinetic and toxicology studies in mice, rats and dogs indicate the drug is readily bioavailable via the inhaled route with little or no accumulation after 14-day dosing and is excreted in the faeces with a $t_{1/2}$ of approximately 6 h. The human starting dose is 0.15mg. Given the NOAEL's in mouse and dog studies, this FIM dose is over 100-fold below the industry accepted safe starting dose. Given the lack of adverse effects seen in the two species, no direct anticipated adverse drug specific side effects are expected in man nor are any drug interactions anticipated given the clear cytochrome profiling. Further details regarding non-clinical pharmacokinetic, safety pharmacology and toxicology data can be found in the IB^[11].

GB-HV-01 Clinical Study Protocol Confidential RD 676/25641 Version: FINAL 6.0 / 05 April 2016 Page 44 of 73

If unacceptable safety findings are identified or if there is any indication that it is not possible to maintain an ample safety margin with higher doses in subsequent cohorts the dose escalation will be stopped or modified accordingly. Subsequent doses therefore may vary from those planned depending on safety and pharmacokinetic results. If the dose escalation stopping criteria for Part 1 in section 9.2.3 are met, then the dose level that was tested will not be repeated or exceeded, however a lower dose may be given following discussion between the Sponsor and the Investigator.

The selection of the 3mg starting dose for **Part 2** was determined based upon interim safety and PK data from **Part 1** (in single doses up to 10mg) and on pre-clinical efficacy and safety data. The highest acceptable dose level in Part 1 of the study will not be exceeded in Part 2.

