- 7. Spirometry to be performed on Day 14 **prior** to BAL sampling procedure.
- 8. Subjects will be dosed with the IMP at the Clinical Centre during clinic visits and will self administer the IMP on non clinic visit days.
- 9. PK blood sampling will be taken on Day 1 prior to dosing = 0h and then at 15min, 30min, 45min, 1h, 2h, 3h, 4h, 5h, 6h and 12h post-dose; Day 2, 3 and 7 prior to dosing = 0h; Day 14 prior to dosing = 0h and then at 15min, 30min, 45min, 1h, 2h, 3h, 4h, 5h, 6h, 12h and 24h post-dose.
- 10. Blood sampling for pharmacogenetic analysis (mRNA) and peripheral blood flow cytometry will be taken Day 1 prior to dosing = 0h and then at 30 min post-dose, Day 7 at 2h post-dose and Day 14 prior to dosing = 0h and then at 30 min post-dose.
- 11. Blood sampling for pharmacogenetic analysis of peripheral blood mononuclear cells (PBMCs) will be taken Day 1 prior to dosing = 0h and Day 14 at 30 min post-dose.
- 12. Blood sampling for Galectin-3 analysis will be taken on Day 1 prior to dosing = 0h and then at 5h post-dose, Day 7 (anytime) and Day 14 prior to dosing = 0h.
- 13. Exhaled Breath Condensate to be performed on Day 14 between 1h and 2h post-dose.
- 14. BAL to be performed on Day 14 between 1h and 4h post-dose. (It is essential post treatment bronchoscopy is performed in the morning.)

GB-HV-01 Clinical Study Protocol Confidential RD 676/25641 Version: FINAL 6.0 / 05 April 2016 Page 51 of 73

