9.9.1.3 Description of Statistical Methods

Simbec Research Limited will carry out the statistical analysis. Full details of the statistical analyses of the data will be documented in an agreed statistical analysis plan, which will be finalised prior to locking the database and subsequent analysis of the study data.

The pharmacokinetic parameters of TD139 in plasma will be determined from the individual concentration versus time data using WinNonlin Phoenix 32. For the calculation of derived pharmacokinetic parameters, concentrations below the limit of quantification (BLQ) will be assigned a value of zero. In case of a deviation from the theoretical time, the actual time of blood sample will be used in the calculation of the derived pharmacokinetic parameters.

Derived pharmacokinetic parameters of TD139 in plasma will be listed and summarised for each treatment. The descriptive statistics presented will be N, n, arithmetic mean, arithmetic standard deviation (SD), coefficient of variation (CV%), minimum, median, maximum and geometric mean (with the exception of t_{max}). The results for t_{max} will be reverted back to the nominal time.

Mean and individual plasma concentration-time curves of TD139 in plasma will be presented for each dose on both linear and semi-logarithmic scales.

Statistical analysis will be performed using SAS® version 9.1.3 or higher.

Dose-Proportionality/Independence: Dose proportionality will be assessed by performing a regression analysis of the log-transformed C_{max} , AUC_{0-t} and AUC_{0-inf} values versus the log-transformed dose using the power model with a fixed effect for dose and a random effect for subject. For each parameter a point estimate and 95% confidence interval will be calculated for the slope of the regression line.

The power model is defined as:

$$log_e(C_{max}, AUC_{0-t}, AUC_{0-inf}) = \alpha + \beta log_e(Dose) + \varepsilon$$
,

where α is the intercept, β is the slope and ϵ is the error term.

Dose independence will be assessed for t½ and CL/F by performing a regression analysis of the untransformed parameters versus dose with a fixed effect for dose and a random effect for subject. For each parameter a point estimate and corresponding 95% confidence interval will be calculated for the slope of the regression line.

Derived pharmacokinetic parameters will be presented graphically for mean C_{max} , AUC_{0-t} , AUC_{0-inf} , $t^{1}/_{2}$ and CL/F versus dose.

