The same analysis will be carried out (for C_{max} , AUC_{τ} , $t\frac{1}{2}$ and CL/F) for Part 2 of the study on Days 1, 7 and 14.

GB-HV-01 Clinical Study Protocol Confidential RD 676/25641 Version: FINAL 6.0 / 05 April 2016 Page 62 of 73

Accumulation Assessment: Log-transformed trough levels at pre-dose on Day 2 through to Day 14 will be used to establish any accumulation of TD139. The ratio of trough concentrations on each consecutive day will be presented and summarized along with a 90% confidence interval. The analysis will be done for each dose level.

Assessment of Steady State: Log-transformed trough concentration levels at pre-dose on Days 7, and 14 will be subjected to mixed effects ANOVA with study day as a fixed effect and subject as a random effect in order to establish whether and when steady state has been attained for each dose level. Back-transformed ratios for the Day 14/Day 7, comparisons will be presented along with corresponding 90% CI.

Additional PK Assessments:

Alveolar macrophage and BAL fluid concentrations of TD139 will be presented as a data listing.

Drug compartment measurements in BAL and alveolar macrophages will be analysed as per the method set out in the study by Naderer *et al*^[1] (e.g. TD139AM = TD139pellet/VAC [where the volume of alveolar cells - VAC, is estimated at 2.42μ l/106 cells])^[1].

PD Assessments:

Macrophage morphology parameters (*ex-vivo* macrophage function and BAL soluble markers) will be presented as a data listing.

Exhaled breath condensate data will be presented as a data listing.

Descriptive statistics of absolute and change from baseline for peripheral blood flow cytometry data will be presented at each time point by dose.

Descriptive statistics of absolute and change from baseline for Galectin-3 plasma concentration data will be presented at each time point by dose.

PG Assessments:

Macrophage phenotypic, mRNA pattern expression analysis from BAL and analysis of peripheral blood mononuclear cells for IPF gene signatures will be presented as a data listing.

Descriptive statistics of absolute and change from baseline of mRNA expression levels from blood leucocytes will be presented at each time point by dose.

Safety Assessments:

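### CL/F is defined only as Dose/AUC0-inf, which understates clearance on Part 2 Day 14, and the Day 7 analysis is planned on a single pre-dose sample

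*Protocol*

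**What the plan says.** Section 9.9.1.1 lists the PK variables for both parts of the study. CL/F has a single entry: "Plasma clearance, calculated as Dose" over AUC0-inf, with no restriction to single dosing. AUC0-inf is "The area under the curve (AUC) extrapolated to infinity from dosing" time. The same list has AUC0-tau, defined from "time of dosing to time t at steady state", but CL/F is not linked to it.

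Section 9.9.1.3 states: "Dose independence will be assessed for t½ and CL/F by performing a regression analysis of the untransformed parameters versus dose". It then repeats the dose-proportionality and dose-independence analyses for Cmax, AUCtau, t½ and CL/F "for Part 2 of the study on Days 1, 7 and 14". AUCtau takes the place of AUC0-t and AUC0-inf for Part 2, while CL/F carries over unchanged.

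Footnote 9 to Table 9.7.2 sets the Part 2 PK sampling. Day 1 has a profile to 12 h. The footnote continues: "Day 2, 3 and 7 prior to dosing = 0h; Day 14 prior to dosing = 0h and then at 15min", with the Day 14 profile running to 24 h.

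**The concern.** There are two faults.

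**Day 14 formula.** Clearance is one dose divided by the area that this dose produces. After a single dose that area is AUC0-inf. After repeated dosing, AUC0-inf measured from the last dose also includes the residue of every earlier dose, while the numerator is still one dose. The quotient is then too low. At steady state the area that matches one dose is AUC0-tau. If the formula is applied as written, CL/F falls between Day 1 and Day 14 even when clearance is constant, and a reader could take this for time-dependent clearance in patients with IPF. More subjects would not remove the error, because it is systematic.

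**Day 7 analysis.** Four parameters are to be analysed on a day with one pre-dose sample. A single trough gives no observed peak, no area over the interval, no terminal slope and hence no clearance.

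**Working it through.** The protocol gives no numerical CL/F to reproduce, so the check is of the formula against the dosing and sampling schedules.

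**Inputs from the protocol**
- Dosing once daily for 14 days (section 9.1): tau = 24 h, 14 doses.
- CL/F = Dose/AUC0-inf (section 9.9.1.1).
- Sampling times from Table 9.7.2, footnote 9: 0, 0.25, 0.5, 0.75, 1, 2, 3, 4, 5, 6, 12 and 24 h. The Day 1 24 h point is the Day 2 pre-dose sample.
- Half-life of about 6 h, from animal studies, with "little or no accumulation after 14-day dosing and is excreted in the faeces" (section 9.6.7).

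**Assumptions**
- Linear, time-constant kinetics in one compartment.
- The protocol gives no human half-life, so 4, 8, 12 and 24 h are shown as assumed values beside 6 h.
- First-order absorption with ka of 1 and 3 per h (assumed) in the absorption model.

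**Step 1: closed form.** By superposition, ignoring the absorption phase, AUC0-inf after dose 14 = R14 × F·Dose/CL, where

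R14 = (1 − 2^(−14·24/t½)) / (1 − 2^(−24/t½)).

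The formula therefore returns (CL/F)/R14, and the understatement is close to 2^(−24/t½). At t½ = 6 h the numerator is effectively 1 and the denominator is 1 − 2^(−4) = 0.9375. So R14 = 1.0667 and the formula returns 0.9375 of true CL/F, an understatement of 6.25%. At steady state AUC0-tau = F·Dose/CL, so Dose/AUC0-tau returns CL/F without this bias.

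**Step 2: absorption model.** At steady state (reached by Day 14 at the half-lives tabulated below), with k = ln 2/t½ and V and F set to 1,

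AUC0-inf per unit dose = [ka/(ka − k)] × [1/(k(1 − e^(−24k))) − 1/(ka(1 − e^(−24ka)))].

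At t½ = 6 h, k = 0.1155. With ka = 1 this is 1.1306 × (9.233 − 1.000) = 9.309. Multiplied by k it is 1.075, and 1/1.075 = 0.930: an understatement of 7.0%. With ka = 3 it is 6.5%.

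**Step 3: the protocol's sampling times.** Linear-trapezoid NCA was applied to the same model at the times listed above, with the terminal slope from the last three points. The Day 14/Day 1 ratio of reported CL/F should be 1, because true clearance is constant. Paired values are for ka = 1; 3 per h.

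| t½ | Understatement, closed form | Understatement, absorption model | Day 14/Day 1 ratio, AUC0-inf on both days | Day 14/Day 1 ratio, AUC0-tau on Day 14 |
|---|---|---|---|---|
| 6 h (animal) | 6.25% | 7.0%; 6.5% | 0.930; 0.935 | 0.997; 0.997 |
| 8 h (assumed) | 12.5% | 13.5%; 12.8% | 0.865; 0.872 | 0.996; 0.996 |
| 12 h (assumed) | 25% | 26.1%; 25.4% | 0.739; 0.746 | 0.997; 0.996 |

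In closed form, an assumed 4 h gives 1.6% and an assumed 24 h gives 50%.

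**Step 4: Day 7.** Counting the samples in footnote 9 gives 1 on Day 7 (pre-dose) and 12 on Day 14. One concentration per subject supports none of Cmax, AUCtau, t½ or CL/F. It does support the trough-based accumulation analysis and the Day 14/Day 7 steady-state ratio, both already planned in section 9.9.1.3.

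**The case against.** **The bias is small on the protocol's own figures.** At about 6 h, with little accumulation in animals, it is 6 to 7%. The larger values need an assumed longer half-life, and at an assumed 4 h it is under 2%. This stands, and it limits the weight of the point. The direction of the error does not depend on half-life.

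**No planned inference changes.** Dose independence is judged from the slope of CL/F on dose within a day. If half-life does not vary with dose, every dose level carries the same proportional bias and a true zero slope stays zero. Accumulation and steady state are judged from troughs, which the formula does not touch. This also stands. What remains is a wrong reported value and a misleading contrast between days.

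**The SAP could set a day-specific formula.** Section 9.9.1.3 does refer full details to an SAP. But the protocol does not leave the point open: it states one unqualified formula and names the analysis days. An SAP that put this right would depart from the protocol.

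**AUC0-tau is not perfect either.** With no samples between 6 and 12 h or between 12 and 24 h, the linear trapezoid overstates area. At 6 h, Dose/AUC0-tau on Day 14 comes out about 4% below true CL/F. Day 1 CL/F carries nearly the same error, so it cancels in the ratio between days. A Day 14 24 h sample below the limit of quantification would be set to zero, so the end of the interval may be less well determined than the schedule suggests. Neither point favours AUC0-inf, which has the same trapezoid error and adds the carry-over.

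**The Day 7 fault reveals itself.** No number can be computed, so no wrong number can be reported. That is true, but the plan still promises analyses that its sampling cannot support. Sampling times may be modified after an interim review, but no post-dose sampling on Day 7 is stated.

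**Conclusion.** Both faults hold as written. Under linear kinetics Dose/AUC0-inf must understate CL/F on Day 14. The size rests on the one-compartment model and on a human half-life that the protocol does not give: 6 to 7% at the animal value of about 6 h, and more if the half-life in patients is longer. The Day 7 contradiction needs no model. The consequences are confined to secondary PK reporting, and the primary safety objective is untouched. The change should be made before the PK analysis, but it does not threaten the study.

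**What to change.** - In section 9.9.1.1, define CL/F as Dose/AUC0-inf for Part 1 and Part 2 Day 1, and as Dose/AUC0-tau for Part 2 Day 14.
- In section 9.9.1.3, limit the Part 2 analyses of Cmax, AUCtau, t½ and CL/F to Days 1 and 14. Keep the Day 7 pre-dose value for the accumulation and steady-state analyses. This reconciles the text with footnote 9 of Table 9.7.2 as it stands. If a Day 7 profile was in fact intended, the flow chart is what disagrees, and the sponsor should say so.

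The cost is protocol and SAP wording plus programming. AUC0-tau is already a listed variable and the Day 14 samples to 24 h are already scheduled, so no extra blood is needed.
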